#### **4. STUDY INTERVENTION**

Patients who are eligible to participate in the trial will be randomized (1:1 allocation) to one of two study arms, and they will take daily:

1. Low Dose Quadruple Therapy (LDQT) comprising candesartan 2 mg, amlodipine 1.25 mg, indapamide 0.625 mg, and bisoprolol 2.5 mg  
OR
2. Candesartan 8 mg

The LDQT includes quarter standard doses of four blood pressure lowering medications, which are currently approved by the US Food and Drug Administration for the treatment of hypertension. The active comparator follows current clinical practice guidelines for the majority of Americans, initiating treatment with an angiotensin II receptor blockers (ARB), which has the best side effect profile of any blood pressure lowering therapy. In both arms, if blood pressure is not controlled (SBP > 130 mmHg or DBP > 80 mmHg) at the six-week follow-up assessment, then study staff will provide participants with an open label pill of amlodipine 5 mg to supplement their study drug, which may be relevant to participants from some race/ethnic groups, including African-Americans. The combination of a calcium channel blocker with an ACE-inhibitor has been demonstrated to be more effective in reducing cardiovascular events than the combination of a thiazide-like diuretic with an ACE-inhibitor based on the ACCOMPLISH trial.

All study drugs, including LDQT, active comparator, and amlodipine add-on will be stored, controlled, and administered centrally. Control of drugs is described in full in the detailed Manual of Procedures. Drug product used in this study is subject to regulatory review and approval through an investigator-initiated investigational new drug (IND) process. Prior to use in human subjects, IND approval will be required.

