2. STUDY OUTCOMES

In the sections below, we include the relevant specific field names for variables within the study database as of the time of SAP creation. These are indicated by the [brackets].

Primary Outcome

Primary efficacy outcome is **mean change (from baseline) in automated office systolic blood pressure (SBP) at 12 weeks** [sbpavg], and analyses will compare this change across arms for primary outcome analyses, adjusting for baseline.

Secondary Outcomes

Secondary efficacy outcomes include:

- 1) Mean automated office SBP at 12 weeks, adjusted for baseline values [sbpavg].
- 2) **Other BP measures** that will be compared across arms, controlling for baseline values:
 - a. Mean change (from baseline) in automated office SBP [sbpavg] at six weeks.
 - b. Mean automated office SBP [sbpavg] at six weeks.
 - c. Mean change (from baseline) in automated office DBP [dbpavg] at six and 12 weeks.
 - d. Mean automated office DBP [dbpavg] at six and 12 weeks.
 - e. Proportion of patients with hypertension control (SBP < 130 mmHg and DBP < 80 mmHg) at six and 12 weeks [sbpavg, dbpavg].
 - f. Proportion of patients requiring step-up treatment [amlo_dispnd].
 - g. Proportion of patients with adverse event-free hypertension control (SBP < 130 mmHg and DBP < 80 mmHg [sbpavg, dbpavg]). For the purposes of this outcome, we will define adverse event-free as absence of any events that are documented as either possibly, probably, or definitely related to study medication ([saerelate] = 3, 4, 5).
- 3) **Medication adherence:** proportion of participants deemed adherent to study medication based on the 80% criterion (i.e., participant took at least 80% of assigned study medication). This information will be captured via:
 - a. Objective pill counts [capsret6, lost6, capsret12, lost12], and
 - b. Self-reported measures [forget, miss30, miss7] in addition to the objective pill counts.
- 4) **Health-related quality of life:** Mean change from baseline in health-related quality of life

using PROMIS Global Health instrument [global01—global10]. There are two domains within this construct:

- a. Global Mental Health (assessed via a T-score)
- b. Global Physical Health (assessed via a T-score)

Safety Outcomes

We plan to evaluate the following safety outcomes:

- 1) Proportion of participants with *any* SAE according to the Good Clinical Practice (GCP) definition [sae_present, saedeath, saelifethrt, saehosp, saedisp, saecong, saeimpevnt].

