We will use simple sample Pearson correlation coefficients (and 95% confidence limits), Bland-Altman plots, or both to examine agreement among continuous outcome measures (primarily focused on office SBP and 24-hour SBP measures). Though these analyses are not the primary focus of this trial and its results, we will use agreement analyses to make inference regarding quality of SBP measurement methods and variability.

Analyses Contingent on Add-on Therapy Requirements

If there is evidence of a difference in proportion of participants requiring amlodipine add-on therapy at six weeks across arms, then we will also explore dividing the sample into four strata: (1) those that required amlodipine add-on treatment + received active control, (2) those that required add-on + received LDQT, (3) those that did not require add-on + received active control, and (4) those that did not require add-on and received LDQT. Depending on cell counts, we will attempt a series of exploratory analyses for key outcomes (SBP, DBP) to evaluate an effect. Additional analyses of this nature will be indicated as exploratory.

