8. POWER AND SAMPLE SIZE CONSIDERATIONS

The initial sample size calculations called for a total of 365 participants to be randomized (1:1 allocation). We anticipated an analytic sample size of 292 based on 365 participants at randomization and a 20% dropout rate by the 12-week follow-up time point. We originally based sample size and power calculations conservatively on an independent two-sample t-test. Based on results of interim analyses (refer to Section 10 for details), we updated our recruitment target to 87 participants (1:1 allocation). The analytic sample size of 77 is anticipated based on 87 participants at randomization.

and a conservatively estimated 12% dropout rate by the 12-week follow-up time point based on 8% dropout rate observed through September 2021.

The initial, conservative plan for primary outcome analyses involving an independent two-sample t-test provided an estimated 80% power to detect a 5 mmHg difference in SBP between the intervention and comparator arms assuming a two-sided 5% level of significance and a 15 mmHg standard deviation in outcome. This estimate is based on a 2017 Cochrane systematic review update evaluating the effects of fixed-dose combination therapy and systematic review on quarter dose combination therapy, and a pilot trial of quarter-dose combination therapy [3]. We assumed baseline SBP has a moderate correlation with follow-up SBP ($r \approx 0.50-0.6$); under this assumption, sample size calculations based on ANCOVA has the potential to allow for over 90% power under the same assumptions for remaining parameters.

At the request of the DSMB, we conducted an interim conditional power analysis, taking into consideration information from both the QUARTET USA trial data as of August 2021 and further the QUARTET (Australia) results.¹⁰ These interim analyses, incorporating information to date, suggested that a recruited sample size of at least 77, and a 12% dropout rate, would provide over 90% conditional power based on a sample of 87 randomized participants.

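### Arm comparisons within the four arm-by-add-on strata are not randomised comparisons, because week-6 blood pressure, which the study drug affects, decides who gets add-on

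*SAP*

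**What the plan says.** Protocol section 4 provides open-label amlodipine in either arm "if blood pressure is not controlled (SBP > 130 mmHg or DBP > 80 mmHg) at the six-week follow-up assessment". Needing step-up treatment is itself an outcome compared by arm (Protocol section 3.2, item 2f; SAP section 2).

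SAP section 6, under the heading on analyses contingent on add-on therapy, sets a trigger: "If there is evidence of a difference in proportion of participants requiring amlodipine add-on therapy at six weeks across arms". If it is met, "then we will also explore dividing the sample into four strata": control with add-on, LDQT with add-on, control without, LDQT without. Subject to cell counts, "we will attempt a series of exploratory analyses for key outcomes (SBP, DBP) to evaluate an effect". The SAP adds that "Additional analyses of this nature will be indicated as exploratory". It names no contrast, estimand or model for this step, and no method for selection after randomisation. Section 9 lists the analysis among the version 2.0 additions.

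The main analyses use the arm as randomised in the mITT set (SAP section 7), and section 6 already reports between-arm differences at both six and 12 weeks.

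**The concern.** Add-on use is a consequence of week-6 pressure, and week-6 pressure is a consequence of treatment. If LDQT lowers pressure more, an LDQT participant who is still above the threshold is on average harder to control than a control participant above it. The same holds below the threshold: LDQT brings under it some participants who would have stayed above it on the comparator. Within each add-on level the LDQT group then carries the worse underlying risk, and randomisation no longer protects the comparison. Adjusting for baseline pressure removes only the part of the imbalance that baseline explains.

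The trigger makes this worse, since the analysis runs only when the data suggest that treatment has changed who gets add-on. A reader shown LDQT against control with and without amlodipine is likely to take the differences as drug effects free of the add-on. They are not.

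**Working it through.** **The plan's own figure.** The documents give no figure for the strata analysis. The nearest stated figure is the original design, which "provided an estimated 80% power to detect a 5 mmHg difference in SBP between the intervention and comparator arms". Its inputs, in SAP section 8, were a 5% two-sided test and an SD of 15 mmHg. With 292 analysed (146 per arm): 5 / (15 × √(2/146)) = 5 / 1.756 = 2.85, and Φ(2.85 − 1.96) = 0.81. The stated 80% is reproduced, so I use SD 15 for follow-up SBP.

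**Inputs from the documents.**
- Effect 6.9 mmHg and baseline SD 13 (Australian sister trial, Protocol section 2.3).
- Correlation of baseline with follow-up SBP 0.5 to 0.6 (SAP section 8).
- A standard-dose single drug lowers SBP by 6 to 9 mmHg (Protocol section 2.1); 7.5 is the stand-in for add-on.
- 77 analysed, that is 38.5 per arm (SAP section 8).

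**Assumptions not in the documents.** Control week-6 mean 132 mmHg (128 to 136 also run), week-6 to week-12 correlation r of 0.5 to 0.8, normal SBP, an SBP-only add-on rule (above 130) fully followed, the same drug effect in everyone, and the same add-on effect in both arms.

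**Step 1, add-on rates.** Control: z = (130 − 132)/15 = −0.133, so 55.3% get add-on. LDQT mean 125.1: z = 0.327, so 37.2%.

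**Step 2, selection within strata.** With φ the normal density, the mean of week-6 SBP above the threshold lies λ = φ(z)/(1 − Φ(z)) SDs above the arm mean.
- Control λ = 0.395/0.553 = 0.715; LDQT λ = 0.378/0.372 = 1.017; gap 0.302.
- Below the threshold, κ = φ(z)/Φ(z): control 0.885, LDQT 0.602; gap 0.282.

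**Step 3, lost baseline balance.** At a baseline correlation of 0.55, LDQT participants start higher by 0.55 × 13 × 0.302 = 2.2 mmHg in the add-on stratum and by 0.55 × 13 × 0.282 = 2.0 mmHg in the other.

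**Step 4, unadjusted week-12 difference.** This is −6.9 + 15 × r × gap. At r = 0.7:
- add-on: −6.9 + 15 × 0.7 × 0.302 = −3.7 mmHg;
- no add-on: −6.9 + 15 × 0.7 × 0.282 = −3.9 mmHg.

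**Step 5, baseline-adjusted difference.** By simulation (2,000,000 participants per scenario), control week-6 mean 132:

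| Baseline correlation | r | Add-on | No add-on |
|---|---|---|---|
| 0.50 | 0.5 | −5.5 | −5.7 |
| 0.55 | 0.7 | −4.7 | −4.9 |
| 0.60 | 0.8 | −4.3 | −4.5 |

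Other control means and pairings of the correlations give about 4 to 6 mmHg overall. Against 6.9 this is a shortfall of about 0.9/6.9 = 13% to 2.9/6.9 = 42%. With a true effect of zero the differences are zero.

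**Step 6, comparisons that keep randomisation.** The week-6 arm difference in all participants returns 6.9. The overall week-12 difference is 6.9 − 7.5 × (0.553 − 0.372) = 5.5 mmHg, diluted because more controls receive amlodipine. At r of 0.7 or more the strata estimates fall below even this figure, so they would suggest that accounting for add-on shrinks the effect, when in this model add-on masks part of it.

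**Step 7, direction.** If the add-on effect differs by arm, the add-on stratum shifts by that difference. From a 5.0 mmHg difference under equal add-on effects of 7 mmHg (control week-6 mean 133), an effect of 4 in LDQT gives 5.0 − 3 = 2.0, and 10 gives 5.0 + 3 = 8.0, above the true 6.9.

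**Step 8, trial size.** At a control mean of 132 the cells are 38.5 × 0.553 = 21, 38.5 × 0.372 = 14, and 17 and 24 without add-on. If the trigger is read as a 5% test, it fires in about 21% of trials with a true effect of 5 mmHg and 34 to 36% with 6.9.

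**The case against.** The case for leaving the text alone has real weight. The analysis is conditional, depends on cell counts and is labelled exploratory; no trial conclusion rests on it. The SAP does not say that arms will be compared within add-on level, nor that the aim is to learn how far add-on masks the drug effect. The four groups might only be summarised. With standard errors of about 4 mmHg within strata, a bias of around 2 mmHg would be hard to see in one trial.

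Most of this stands as a limit on importance. It does not remove the problem. An exploratory label warns of multiplicity and low precision, not of systematic bias. Comparing arms within add-on level is the natural use of four arm-by-add-on groups meant to evaluate an effect, and nothing in the SAP rules it out.

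Three stronger readings should be resisted.
- A reader might infer that the strata must understate the drug effect. That needs equal add-on effects in both arms. LDQT already contains amlodipine and the comparator does not (Protocol section 4), so equality is not given, and step 7 shows that the error can go either way.
- A reader might infer that bias is present exactly when the trigger fires. At this size a 5% trigger would fire in about 5% of trials with no drug effect and no bias, and would miss most trials with a true effect of 6.9.
- A reader might infer that the main result is compromised. It is analysed by randomised arm whatever the add-on use.

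**Conclusion.** The concern holds as a limited one. Any comparison of arms within an add-on level conditions on a variable that follows randomisation and that treatment affects. It is biased whenever the drug lowers week-6 pressure, and unbiased if the drug has no effect there. That much follows from the add-on rule and needs no simulation.

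The size is illustrative: about 4 to 6 mmHg, baseline-adjusted, for a true 6.9, under the constant-effect, equal-add-on model and the assumed correlations. If the strata models follow the SAP's two-visit mixed model, the week-6 part is cut further, to about 2.6 to 3.8 mmHg, because week-6 pressure defines the strata. The documents settle neither size nor direction. The consequence is a misleading supportive result. The change is worth making because it costs little.

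**What to change.** In SAP section 6, replace the strata analyses with a descriptive table of the four groups: counts, baseline, week-6 and week-12 SBP and DBP. Give no between-arm test or estimate within add-on level, and state that such differences are not causal effects of the study drug because add-on is decided by week-6 pressure. Name the randomised week-6 arm difference, measured before any add-on, as the add-on-free comparison. It is already a planned secondary outcome.

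An analysis that sets week-12 pressure after add-on to missing and imputes it within arm should be optional at most, and labelled as extrapolation. Under the add-on rule no participant above the threshold has an add-on-free week-12 value, so the imputation model has nothing to learn from there. At the step 1 rates it would cover (55.3% + 37.2%)/2 = 46% of about 77 participants.

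The cost is a few sentences in the SAP and the loss of the exploratory strata models. The week-6 contrast describes the effect at six weeks, so the 12-week effect without add-on stays unestimated.

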7. ANALYTIC DATASET

Analyses will include the (modified) intention-to-treat (mITT) dataset, whereby all those participants with data at any follow-up time point and baseline to contribute to analyses will be included in analyses according to arm to which they were randomized, regardless of adherence to the study protocol. We will conduct a sensitivity analysis on the per protocol dataset (defined as 80% treatment regimen adherence) since precise estimates of intervention effect (if any) on outcomes are important in a phase II study.

Power and sample size considerations allowed for some missing data (20%); however, in the event of large amounts of missing data (i.e., more than 10%), multiple imputation analyses will be explored. We will examine rates of missing data for all variables and determine whether the rates vary by participant characteristics, etc. These summarizations will inform potential biases resulting from missing data. Mixed effects models planned for longitudinal analysis are generally robust for unbalanced data across study time points. Additional sensitivity analyses will explore multiple imputation methods and the global sensitivity analysis to evaluate overall trial robustness [2]. These analyses will again serve as sensitivity analyses to the previously outlined analyses.

8. POWER AND SAMPLE SIZE CONSIDERATIONS

The initial sample size calculations called for a total of 365 participants to be randomized (1:1 allocation). We anticipated an analytic sample size of 292 based on 365 participants at randomization and a 20% dropout rate by the 12-week follow-up time point. We originally based sample size and power calculations conservatively on an independent two-sample t-test. Based on results of interim analyses (refer to Section 10 for details), we updated our recruitment target to 87 participants (1:1 allocation). The analytic sample size of 77 is anticipated based on 87 participants at randomization.

and a conservatively estimated 12% dropout rate by the 12-week follow-up time point based on 8% dropout rate observed through September 2021.

The initial, conservative plan for primary outcome analyses involving an independent two-sample t-test provided an estimated 80% power to detect a 5 mmHg difference in SBP between the intervention and comparator arms assuming a two-sided 5% level of significance and a 15 mmHg standard deviation in outcome. This estimate is based on a 2017 Cochrane systematic review update evaluating the effects of fixed-dose combination therapy and systematic review on quarter dose combination therapy, and a pilot trial of quarter-dose combination therapy [3]. We assumed baseline SBP has a moderate correlation with follow-up SBP ($r \approx 0.50-0.6$); under this assumption, sample size calculations based on ANCOVA has the potential to allow for over 90% power under the same assumptions for remaining parameters.

At the request of the DSMB, we conducted an interim conditional power analysis, taking into consideration information from both the QUARTET USA trial data as of August 2021 and further the QUARTET (Australia) results.¹⁰ These interim analyses, incorporating information to date, suggested that a recruited sample size of at least 77, and a 12% dropout rate, would provide over 90% conditional power based on a sample of 87 randomized participants.

Previously, the protocol required the 24-hour ambulatory blood pressure assessments, and we thus conducted initial power calculations based on several a priori assumptions for this endpoint as follows: Since expected mean 24-hour ambulatory blood pressure may be more precise than office blood pressure (with a standard deviation of 12 mmHg vs. 15 mmHg for office blood pressure), we estimate over 95% power with the planned sample size to detect a 5 mmHg difference across arms in this important secondary outcome, under the same assumptions as outlined for our primary outcome (office blood pressure). However, subsequent protocol modifications allowed for optional 24-hour ambulatory blood pressure, and this outcome has been modified to become an exploratory outcome.

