In August 2021, the QUARTET (Australia) trial compared the effect of irbesartan at 37.5 mg, amlodipine at 1.25 mg, indapamide at 0.625 mg, and bisoprolol at 2.5 mg with irbesartan 150 mg daily among 591 patients with mild to moderate hypertension who had a baseline mean (SD) systolic blood pressure of 142 (13) mmHg in the intervention group and 140 (13) mmHg in the control group. Compared with the irbesartan control group, patients randomized to the quadpill had a 6.9 mmHg (95% CI: 4.9-8.9) greater systolic blood pressure lowering at 12 weeks. These results were sustained up to 12 months in a sample of 417 patients who were followed for 12 months when the difference was 7.7 mmHg (95% CI: 5.2-10.3) of systolic blood pressure. Dizziness was reported among 93 (31.0%) patients in the intervention group compared with 74 (25.4%) patients in the control group (RR 1.27 [95% CI: 0.98-1.64]). There were no serious adverse events due to syncope, falls, or acute kidney injury. The study participants were largely White (82%) and Asian (12%) race/ethnicity. Thus, there is promising evidence of an ultra-low-dose combination approach, but additional data are needed in more diverse populations.

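### Protocol 16.1 rests the reduced target of 87 on a two-sample t-test and follows it with 80% power at 5 mmHg; that power belongs to the superseded design, and with 77 analysed the same test has about 30%

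*SAP*

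**What the plan says.** Protocol 16.1 opens with the current target: 87 randomised, 77 expected in the analysis after 12% dropout. It then says that this sample size rests, conservatively, on an independent two-sample t-test, and that the planned mixed model will add precision. Its next paragraph, headed as the initial calculation, gives "80% power to detect a 5 mmHg difference in SBP between the intervention and comparator arms". The inputs there are SD 15 mmHg and a two-sided 5% test. No sample size is attached to that figure. The original N of 364 appears only in the third paragraph, on ambulatory blood pressure.

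SAP section 8 carries the same power clause but is clearer about its origin: "We anticipated an analytic sample size of 292 based on 365 participants at randomization and a 20% dropout rate". It describes the t-test as the original basis and says that 87 came from interim analyses. It also gives the gain expected from baseline adjustment: "We assumed baseline SBP has a moderate correlation with follow-up SBP", with r about 0.5 to 0.6, for over 90% power under the original design.

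For the reduced target, both documents give one power statement, that the sample "would provide over 90% conditional power based on a sample of 87 randomized participants". They say that it used the trial's own data to August 2021 and the Australian results. Neither gives the assumed effect, the SD, the information fraction, the interim estimate or the weight of the external data. SAP section 10, to which section 8 refers for details, does not supply them. Protocol 2.3 reports that Australian patients on the quadpill "had a 6.9 mmHg (95% CI: 4.9-8.9) greater systolic blood pressure lowering at 12 weeks".

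**The concern.** In Protocol 16.1 a reader meets the 87/77 target, then the t-test named as its basis, then 80% power at 5 mmHg, then a figure over 90%. The natural inference is that a trial of 87 has at least 80% power for 5 mmHg. A t-test calculation that needed 292 analysed patients cannot support 77 with the same effect, SD and power.

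What is at stake is how the result is read. If 5 mmHg were the true benefit, a trial of this size would, under the documents' own SD and correlation and a single-visit analysis, miss significance more often than not. A reader who believes that the power is 80% or more would then take a non-significant result as evidence against the combination.

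**Working it through.** **Inputs.** Two-sided 5%, SD 15 mmHg, effect 5 mmHg, r = 0.5-0.6 (SAP 8). Analysed N: 292 originally, 77 now (SAP 8; 77 also in Protocol 16.1). External effect 6.9 mmHg at 12 weeks and external baseline SD 13 (Protocol 2.3). The correlation between weeks 6 and 12 is in neither document, so it is an assumption here.

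**Formulas.** Residual SD after baseline adjustment: s = SD × √(1 − r²), so s = 15.0 (r = 0), 12.99 (r = 0.5) or 12.0 (r = 0.6). SE = s × √(1/n₁ + 1/n₂). Power comes from the noncentral t with n₁ + n₂ − 2 degrees of freedom and noncentrality effect/SE.

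**1. The original design reproduces.** 365 × 0.80 = 292, or 146 per arm. SE = 15 × √(2/146) = 1.756; 5/1.756 = 2.85; power 81.0% (stated 80%). With r = 0.5 and 0.6, power is 90.6% and 94.4% (stated over 90%).

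**2. The same calculation at the current size.** 87 × 0.88 = 76.6, so 77, split 39 and 38. √(1/39 + 1/38) = 0.228.

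| | SE | Power, 5 mmHg | Power, 6.9 mmHg |
|---|---|---|---|
| r = 0 (t-test), s = 15.0 | 3.42 | 30.3% | 51.3% |
| r = 0.5, s = 12.99 | 2.96 | 38.5% | 63.3% |
| r = 0.6, s = 12.0 | 2.74 | 43.8% | 70.2% |

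**3. Effect of the mixed model.** If the visit terms are dropped, as the plan allows when they are not significant, the arm effect is averaged over two visits. With residual correlation ρ between visits, the variance is multiplied by (1 + ρ)/2. For SD 15:

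| ρ (assumed) | 5 mmHg, r = 0.5 to 0.6 | 6.9 mmHg, r = 0.5 to 0.6 |
|---|---|---|
| 0.3 | 54% to 61% | 81% to 87% |
| 0.5 | 49% to 55% | 76% to 82% |
| 0.7 | 44% to 50% | 70% to 77% |

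If a visit term is significant, the plan makes the 12-week contrast primary and the gain is small.

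**4. A smaller SD.** If the Australian baseline SD of 13 also held at follow-up, r = 0.6 would give 55% at 5 mmHg and 82% at 6.9 mmHg for one visit, and 67% and 91% when pooled with ρ = 0.5. The most favourable combination tried at 5 mmHg (SD 13, r = 0.6, ρ = 0.3) gives 73%.

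**5. The conditional power.** It is Φ{[z₁√t + θ(1 − t) − 1.96]/√(1 − t)}, where z₁ is the interim statistic, t the information fraction and θ the assumed future effect divided by its SE at 77. None of the three is printed, so the figure cannot be recomputed. For illustration, with s = 12 and 6.9 mmHg assumed for the remaining patients, 90% needs an interim difference of about 8.8 mmHg at t = 0.5, 7.7 at t = 0.65 and 6.9 at t = 0.8 (t assumed).

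**The case against.** The strongest reply is that conditional power and unconditional power are different quantities. The plan labels its figure as conditional and says that it uses data to date, and the main input, the August 2021 estimate, is not in the documents. This stands. Setting the results of step 2 against the printed 90% and calling the gap a shortfall would subtract one quantity from another. A reader might also infer that the figure merely reflects a lucky early look. The documents do not support that: the interim differences in step 5 fall within the Australian interval of 4.9 to 8.9 mmHg, and the information fraction is unknown.

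Second, single-visit power understates what the planned model may achieve. This also stands. At 6.9 mmHg, pooled visits with a small enough SD can exceed 90%, so no fixed ceiling can be put on the power of the 87-patient trial. At 5 mmHg, however, no combination tried reaches 80%.

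Third, the 80% figure is already labelled as initial. For SAP 8 this largely answers the point, because the original 365/292 design is set out there as its basis. It does not answer Protocol 16.1, which names the t-test as the basis of the current target before giving the figure without its N.

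Fourth, this is a phase II trial of preliminary efficacy, and confidence limits are already required for every between-arm difference. That limits the harm, but it does not make the sample-size statement correct.

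**Conclusion.** The point holds for how the design is described. The t-test that Protocol 16.1 cites does not give the reduced target 80% power at 5 mmHg; it gives about 30%, or about 38-44% with the SAP's baseline correlation. At 6.9 mmHg the figures are 51% and 63-70%. These rest on SD 15, two-sided 5%, 77 analysed and one follow-up visit. With both visits pooled and an assumed correlation of 0.5 they become about 49-55% and 76-82%; a smaller SD would raise them further.

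A reader might go further and infer that the over-90% conditional power is miscalculated, or that the decision to stop at 87 was unsound. The documents support neither. The figure cannot be reproduced because its inputs are missing, and it is not shown to be wrong. What can be said is that it conditions on interim data and so does not replace a statement of power for a named effect. The reduced design has no such statement that is correct.

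**What to change.** - **Protocol 16.1:** remove or correct the statement that the 87/77 size is based on a two-sample t-test; say that it came from the interim conditional power analysis requested by the DSMB.
- **Both documents:** tie the 80% at 5 mmHg explicitly to the superseded design (365 randomised and 292 analysed in the SAP; N = 364 in the protocol).
- **Both documents:** add power with 77 analysed at 5 and 6.9 mmHg under SD 15 and r = 0.5-0.6 (about 38-44% and 63-70% for one visit), with the assumptions shown. Give any pooled-visit figure as a range over the assumed between-visit correlation, for example 44-61% and 70-87% for 0.3 to 0.7.
- **Conditional power sentence:** keep it as the basis of the DSMB decision; add the effect, SD and information fraction that it assumed, and say that it conditions on the August 2021 interim data.

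Enrolment, conduct and analysis do not change. The cost is a few sentences and a less favourable stated power.
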